## 10.3 SUBGROUP ANALYSIS FOR EFFICACY ENDPOINTS

No subgroup analysis is planned for this study.

## **11.0 SAFETY ANALYSES**

The safety analysis will be performed using the Safety Population. The safety parameters will include adverse events (AEs) and clinical laboratory parameters, vital sign (including postural), electrocardiographic (ECG) parameters, and weight. For each safety parameter of the clinical laboratory, vital signs, weight, and ECG parameters, the last non-missing safety assessment before the first dose of study intervention will be used as the baseline for all analyses of that safety parameter. Continuous variables will be summarized by number of participants and mean, SD, median, minimum, and maximum values. Categorical variables will be summarized by number and percentage of participants.

The safety summaries will be provided by study intervention group for each cohort separately. If any cohort has a similar linaclotide dose with another cohort, the safety summaries will also be provided combining participants from the similar dose cohorts. Summaries will also be provided for participants from all cohorts in the placebo group.

### **11.1 ADVERSE EVENTS**

Adverse events will be coded by system organ class and preferred term using the *Medical Dictionary for Regulatory Activities*, version 23.0 or newer.

An AE will be considered a treatment-emergent adverse event (TEAE) if

- The AE began on or after the date of the first dose of study intervention; or
- The AE was present before the date of the first dose of study intervention, but increased in severity or became serious on or after the date of the first dose of study intervention

An AE that occurs more than 1 day after the last dose of study intervention will not be counted as a TEAE.

An AE will be considered a treatment-emergent serious adverse event (TESAE) if it is a TEAE that additionally meets any serious adverse event (SAE) criterion.

The number and percentage of participants reporting TEAEs in each study intervention group will be tabulated by descending percentage in any group, by system organ class and preferred term, and further categorized by severity and causal relationship to the study intervention. If more than 1 AE is coded to the same preferred term for the same participant, the participant will be counted only once for that preferred term using the greatest severity and strictest causality for the summarization by severity and causal relationship.

For the all screened participants, separate tabular displays will be presented for participants who died, participants with SAEs, participants with AEs leading to premature discontinuation, and participants with AEs of special interest. AEs during the Postintervention Period will also be included in the listings. Listing of all AEs will also be presented.

## 11.2 CLINICAL LABORATORY PARAMETERS

Descriptive statistics for clinical laboratory values (in International System of Units [SI] units) and changes from the baseline values at each assessment time point will be presented by study intervention group within the corresponding cohort for the following laboratory parameters:

Hematology: Absolute and differential white blood cell count, hemoglobin, hematocrit, platelet count, red blood cell count, and red blood cell indices (mean corpuscular volume, mean corpuscular hemoglobin, and mean corpuscular hemoglobin concentration)

Chemistry: Sodium, potassium, calcium, chloride, bicarbonate, magnesium, phosphate, glucose, blood urea nitrogen, creatinine, total protein, alkaline phosphatase (ALP), albumin, total bilirubin (TBL), alanine aminotransferase (ALT), aspartate aminotransferase (AST), total cholesterol

Urinalysis: Specific gravity and pH

If any cohort has a similar linaclotide dose with another cohort, the safety summaries will also be provided combining participants from the similar dose cohorts. Summaries will also be provided for participants from all cohorts in the placebo group.

Clinical laboratory test values will be considered potentially clinically significant (PCS) if they meet either the lower-limit or higher-limit PCS criteria listed in [Table 11.2-1](#). The number and percentage of participants who have PCS postbaseline clinical laboratory values will be tabulated by study intervention for the double-blind Intervention Period within the corresponding cohort. The percentages will be calculated relative to the number of participants with available non-PCS baseline values and at least 1 postbaseline assessment for the double-blind Intervention Period. The numerator will be the total number of participants with available non-PCS baseline values and at least 1 PCS postbaseline value for the double-blind Intervention Period within the corresponding cohort. A supportive tabular display of participants with PCS postbaseline values will be provided, including the PID number, baseline and all postbaseline (including non-PCS) values for all the cohorts. In this listing, any participant with PCS value (if any) during the Post-intervention period will also be included.

In addition, a tabular display showing all AEs that occurred in participants who had PCS postbaseline clinical laboratory values will be provided.

Shift tables from baseline to the end of double-blind Intervention Period for clinical laboratory parameters listed above will be presented by study intervention group within the corresponding cohort for the following categories: low, normal, and high, which are provided by lab vendor.

The PCS summaries for laboratory parameters and shift table from baseline to the end of double-blind Intervention Period will also be provided combining participants from the similar linaclotide dose cohorts (if any) and combining participants from all cohorts in the placebo group.

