8.3.1. Adverse Events of Special Interest (AESIs)

AESIs are defined as significant volume depletion and/or significant electrolyte abnormalities and/or ECG abnormalities that are considered by the investigator or sponsor to be related to diarrhea. The investigator should contact the sponsor if there is any question whether the criterion for an AESIs has been met. All AESIs must be reported to the sponsor as described in Section 10.3.

8.3.2. Time Period and Frequency for Collecting Adverse Events, Serious Adverse Events, and Adverse Events of Special Interest Information

At each visit, participants are to be queried regarding any AEs or SAEs that have occurred since the previous visit. Participants will be asked to volunteer information with a nonleading question such as, "How do you feel since your last visit?" Study site personnel will record all pertinent information in the participant's eCRF. All SAE from the signing of the ICF until 30 days after the last dose of study intervention will be collected at the timepoints specified in the SoA (Section 1.3), and as observed or reported spontaneously by study participants.

All AEs from the signing of the ICF until 30 days after the last dose of study intervention will be collected at the timepoints specified in the SoA (Section 1.3), and as observed or reported spontaneously by study participants.

Medical occurrences that begin before the start of study intervention, but after obtaining informed consent will be recorded in the AE section of the eCRF.

All SAEs and serious AESIs of special interest will be recorded and reported to the sponsor or designee within 24 hours on an SAE form, as indicated in Section 10.3. Non-serious AESIs do not require submission on an SAE form; rather, these events only need to be entered into the eCRF. The investigator will submit any updated SAE data to the sponsor within 24 hours of it being available.

Investigators are not obligated to actively seek AE or SAE information after conclusion of the study participation. However, if the investigator learns of any SAE including a death, at any time after a participant has been discharged from the study, and he/she considers the event to be reasonably related to the study intervention or study participation, the investigator must promptly notify the sponsor.

The method of recording, evaluating, and assessing causality of AEs and SAEs and the procedures for completing and transmitting SAE reports are provided in Section 10.3.

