9.4.2.2. Clinical Laboratory Assessments

Descriptive statistics for clinical laboratory values (in SI units) at baseline (screening) and changes from baseline at each assessment time point will be presented by study intervention group within each cohort.

The criteria for potentially clinically significant (PCS) laboratory values will be detailed in the SAP. The number and percentage of participants who have PCS postbaseline clinical laboratory values within the corresponding cohort during the double-blind study intervention period will be tabulated by study intervention. The percentages will be calculated relative to the number of participants who have available non-PCS baseline values and at least 1 postbaseline assessment for the double-blind Study Intervention Period of the corresponding cohort. The numerator will be the total number of participants with available non-PCS baseline values and at least 1 PCS postbaseline value during the double-blind Study Intervention Period of the corresponding cohort. A supportive listing of participants with PCS postbaseline values will be provided for the safety population.

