10.8.5. Week 4/EOT (Visit 5)

Participants will arrive in a fasted state for this visit after completing at least 28 days of study intervention to receive their last dose of study intervention before or after PK sample. All randomized participants who prematurely discontinue from the study, regardless of cause, are required to be seen for the assessments completed at EOT (Visit 5, Week 4), except for PK sample collection. This visit should be scheduled at approximately the same time as when participants take their daily dose. During Week 4 (Visit 5), the following procedures will be performed:

- IWRS verification
- Perform a physical examination, including general appearance, skin, HEENT (head, ears, eyes, nose, and throat), neck, thorax/lungs, cardiovascular, abdomen, musculoskeletal, lymph

nodes, neurologic (including mental status), and visual inspection of the lumbosacral and perianal region.

- Complete modified Rome III assessment
- Obtain vital signs (weight, temperature (oral, rectal, or tympanic), and respiratory rate) and postural vital signs (supine systolic and diastolic BP, and pulse rate) (Section 8.2.2)
- Obtain standard 12-lead ECG (supine)
- Obtain clinical laboratory tests consisting of clinical chemistry, hematology and urinalysis. All laboratory tests requiring blood draws should be collected at the same time
- Review any AEs occurring since the last visit
- Review concomitant medications
- PK sample will be obtained in participants who will be completing the study intervention at this visit.
- Pre-dose or post-dose PK sampling should be obtained at the same time as clinical lab tests described above to avoid an extra needle stick.
- Pre-dose sample will be obtained from participants assigned to this group at the clinic before the administration of the last dose of study intervention. Post-dose PK sample will be obtained 1-8 hours after the last dose of study intervention in participants assigned to the post-dose PK group. The last dose of study intervention should be administered after confirming the participant has fasted for at least 2 hours. Participants may resume eating 30 minutes after receiving their last dose of study intervention at the study site.
- Obtain date and time of the dose of study intervention prior to PK sample collection
- Obtain standard 12-lead ECG (supine)
- Review use of protocol-permitted rescue medication dispensed in IWRS where applicable.

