**Table 11.2-1 Criteria for Potentially Clinically Significant Laboratory Results**

Parameter	SI Unit	Lower Limit	Higher Limit
CHEMISTRY			
Albumin	g/L	< 0.9 × LLN	> 1.1 × ULN
Alanine aminotransferase (ALT)	U/L	—	≥ 3 × ULN
Alkaline phosphatase (ALP)	U/L	—	≥ 1.2 × ULN
Aspartate aminotransferase (AST)	U/L	—	≥ 3 × ULN
Bicarbonate	mmol/L	< 0.9 × LLN	> 1.1 × ULN
Bilirubin, total (TBL)	μmol/L	—	> 1.5 × ULN
Calcium	mmol/L	< 0.9 × LLN	> 1.1 × ULN
Chloride	mmol/L	< 0.9 × LLN	> 1.1 × ULN
Cholesterol, Total	mmol/L	—	> 1.6 × ULN
Creatinine	μmol/L	—	> 1.3 × ULN
Glucose, random, serum	mmol/L	< 0.8 × LLN	> 1.4 × ULN
Potassium	mmol/L	< 0.9 × LLN	> 1.1 × ULN
Protein, total	g/L	< 0.9 × LLN	> 1.1 × ULN
Sodium	mmol/L	< 0.9 × LLN	> 1.1 × ULN
Urea Nitrogen (BUN)	mmol/L	—	> 1.2 × ULN
HEMATOLOGY			
Basophils, absolute cell count	10  /L	—	> 3 × ULN
Eosinophils absolute cell count	10  /L	—	> 3 × ULN
Lymphocytes absolute cell count	10  /L	< 0.7 × LLN	> 1.3 × ULN
Monocytes, absolute cell count	10  /L	< 0.5 × LLN	> 2.0 × ULN
Neutrophils, absolute cell count	10  /L	< 0.8 × LLN	> 1.5 × ULN
Hematocrit	Ratio	< 0.9 × LLN	> 1.1 × ULN
Hemoglobin	g/L	< 0.9 × LLN	> 1.1 × ULN
Platelet count	10  /L	< 0.5 × LLN	> 1.5 × ULN
Red blood cell count	10  /L	< 0.9 × LLN	> 1.1 × ULN
White blood cell count	10  /L	< 0.7 × LLN	> 1.5 × ULN
URINALYSIS			
pH	—	< 0.9 × LLN	> 1.1 × ULN
Specific gravity	—	—	> 1.1 × ULN

LLN = lower limit of normal value provided by the laboratory; SI = *Le Système International d'Unités* (International System of Units); ULN = upper limit of normal value provided by the laboratory.

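### The only PCS limit for urine specific gravity in SAP Table 11.2-1, above 1.1 × ULN, works out at 1.100 or more and could not be met by any assumed maximum urine reading up to 1.080

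*SAP*

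**What the plan says.** Protocol Section 9.4.2.2 leaves the definition to the analysis plan: "The criteria for potentially clinically significant (PCS) laboratory values will be detailed in the SAP". SAP Section 11.2 then sets the rule, "Clinical laboratory test values will be considered potentially clinically significant (PCS) if they meet either the lower-limit or higher-limit PCS criteria listed in" Table 11.2-1, so a value that meets neither limit is not PCS.

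The table row for this parameter reads "Specific gravity — — > 1.1 × ULN". The two dashes stand in the unit and lower-limit columns. The table footnote defines ULN as the laboratory's own upper limit, and no numeric value is given.

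Section 11.2 takes as denominator the participants with a non-PCS baseline and at least one postbaseline assessment, and as numerator those among them with at least one PCS postbaseline value. PCS status also decides who appears in a supportive listing and in a cross-display: "a tabular display showing all AEs that occurred in participants who had PCS postbaseline clinical laboratory values will be provided". Under SAP Section 16.4 every postbaseline assessment, repeats and unscheduled ones included, counts towards PCS status.

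The one scheduled postbaseline urinalysis is at Week 4/EOT (Protocol Section 10.8.5): "Obtain clinical laboratory tests consisting of clinical chemistry, hematology and urinalysis". Separately from PCS, SAP Section 11.2 plans "Shift tables from baseline to the end of double-blind Intervention Period for clinical laboratory parameters listed above", using the laboratory's low, normal and high categories.

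**The concern.** A 10% multiplier suits a quantity measured from zero. Specific gravity is measured from water at 1.000, and its normal variation lies in the second and third decimals. Multiplying the whole number by 1.1 adds about 0.10, which is several times the full distance from water to a typical upper limit. A criterion like this separates no child from any other.

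What is at stake is how the output reads. No baseline value could be PCS either, so every child with a baseline and a postbaseline value would enter the denominator. The result would be 0/n with a real n, and the figure alone would not show whether the zero was observed or built in. The listing and the adverse-event cross-display would likewise never include a child because of specific gravity.

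**Working it through.** **Inputs.** From the documents: the 1.1 multiplier, the absence of a lower limit and the either-limit rule (SAP Section 11.2 and Table 11.2-1); group sizes (SAP Section 14.0). By definition of the quantity: water = 1.000, so ULN is at least 1.000. Assumed, because the documents give neither: ULN from 1.020 to 1.035, and a highest urine reading from 1.030 to 1.080. The plan derives no figure here that could be reproduced.

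**Step 1, the limit.** Limit = 1.1 × ULN. At the floor, 1.1 × 1.000 = 1.100. The margin above ULN is 0.1 × ULN, set against the whole distance from water to ULN.

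| Assumed ULN | Limit, 1.1 × ULN | Margin, 0.1 × ULN | ULN − 1.000 | Margin ÷ (ULN − 1.000) |
|---|---|---|---|---|
| 1.020 | 1.122 | 0.102 | 0.020 | 5.1 |
| 1.025 | 1.1275 | 0.1025 | 0.025 | 4.1 |
| 1.030 | 1.133 | 0.103 | 0.030 | 3.4 |
| 1.035 | 1.1385 | 0.1035 | 0.035 | 3.0 |

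**Step 2, can it be reached?** A maximum reading M exceeds the limit only if ULN < M ÷ 1.1.

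- M = 1.030: ULN below 0.936
- M = 1.040: ULN below 0.945
- M = 1.060: ULN below 0.964
- M = 1.080: ULN below 0.982

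All of these are below water. Over the assumed range of maxima, no possible ULN makes the row attainable.

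**Step 3, what the table would show.** Full enrolment gives 3 × 6 + 5 = 23 linaclotide and 3 × 2 + 1 = 7 placebo participants. Under the assumptions above, the PCS numerator is 0 in each group, out of up to 23 and up to 7 in total.

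**Step 4, one candidate replacement.** Applying the 10% to the part above water gives the limit 1.000 + 1.1 × (ULN − 1.000). For the four ULNs this is 1.022, 1.0275, 1.033 and 1.0385, which is 0.002 to 0.0035 above ULN. It differs from a plain above-ULN rule only if the laboratory's reporting step is no larger than that margin. With an assumed step of 0.005, the first reportable values above ULN are 1.025, 1.030, 1.035 and 1.040. All of them already exceed the new limit, so the two rules would coincide.

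**The case against.** The strongest case against the point is that little depends on the row. Specific gravity also gets descriptive statistics with minimum and maximum, a low/normal/high shift table and a listing of all assessments. Investigators must review each laboratory report and record clinically relevant changes as adverse events (Protocol Section 8.2.4). Table layouts are specified in a separate document (SAP Section 4.0), so it is not known how a zero row would be displayed. With one scheduled postbaseline urinalysis, after a fast, even a corrected row says little about the preceding four weeks. All of this stands and limits the point to a correction of the table specification. It does not make the criterion usable.

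It is also fair to object that calling the limit unreachable needs a maximum urine reading, which the documents do not give. That is why the claim is stated for a range of maxima.

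A reader might infer something stronger: that volume depletion could go undetected, since the protocol says "AESIs are defined as significant volume depletion and/or significant electrolyte abnormalities and/or ECG abnormalities" and makes relation to diarrhea part of that definition. The documents do not support this. AESI status is a judgement of the investigator or sponsor, it does not use PCS flags, and AESIs have their own display (SAP Section 11.1). Nor is dose escalation compromised. Protocol Section 4.1 bases the decisions between cohorts on DSMB review of all available safety data, and no stated rule uses the specific gravity row.

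**Conclusion.** The criterion is wrong as written, with a narrow effect. For any ULN of at least 1.000 the limit is at least 1.100. If no urine reading goes above 1.080, the highest maximum assumed here, the row is zero in every group whatever the children's actual values. The consequence is confined to the PCS table, its listing and the adverse-event cross-display, and only for this parameter. The laboratory's ULN and the maximum reading are assumptions, but the conclusion does not change across the ranges shown. The point is worth correcting because the correction is cheap and a built-in zero is uninformative. It has no bearing on efficacy, dose selection or AESI assessment.

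**What to change.** Before unblinding, replace the specific gravity row in Table 11.2-1 with an attainable limit that the sponsor sets from the central laboratory's reference range and reporting step. Options, all for analysis flagging only:

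- An additive margin above ULN.
- The table's 10% applied above water: (value − 1.000) > 1.1 × (ULN − 1.000). First check that it differs from a plain above-ULN rule at the laboratory's reporting step and lies within the measuring range.
- The laboratory's high flag. PCS then means the same as high and largely repeats the shift table, except for repeat and unscheduled values.

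Failing these, drop the row so that no structural zero is reported.

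The cost is one table row and trivial programming, with no new data. The downside is a few more flags and adverse-event cross-listings to review. Some may reflect the fast of at least 2 hours before the Visit 5 dose (water is allowed, Protocol Section 10.8.2) and not study drug. That applies to linaclotide and placebo alike.

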**Table 11.2-1 Criteria for Potentially Clinically Significant Laboratory Results**

Parameter	SI Unit	Lower Limit	Higher Limit
CHEMISTRY			
Albumin	g/L	< 0.9 × LLN	> 1.1 × ULN
Alanine aminotransferase (ALT)	U/L	—	≥ 3 × ULN
Alkaline phosphatase (ALP)	U/L	—	≥ 1.2 × ULN
Aspartate aminotransferase (AST)	U/L	—	≥ 3 × ULN
Bicarbonate	mmol/L	< 0.9 × LLN	> 1.1 × ULN
Bilirubin, total (TBL)	μmol/L	—	> 1.5 × ULN
Calcium	mmol/L	< 0.9 × LLN	> 1.1 × ULN
Chloride	mmol/L	< 0.9 × LLN	> 1.1 × ULN
Cholesterol, Total	mmol/L	—	> 1.6 × ULN
Creatinine	μmol/L	—	> 1.3 × ULN
Glucose, random, serum	mmol/L	< 0.8 × LLN	> 1.4 × ULN
Potassium	mmol/L	< 0.9 × LLN	> 1.1 × ULN
Protein, total	g/L	< 0.9 × LLN	> 1.1 × ULN
Sodium	mmol/L	< 0.9 × LLN	> 1.1 × ULN
Urea Nitrogen (BUN)	mmol/L	—	> 1.2 × ULN
HEMATOLOGY			
Basophils, absolute cell count	10  /L	—	> 3 × ULN
Eosinophils absolute cell count	10  /L	—	> 3 × ULN
Lymphocytes absolute cell count	10  /L	< 0.7 × LLN	> 1.3 × ULN
Monocytes, absolute cell count	10  /L	< 0.5 × LLN	> 2.0 × ULN
Neutrophils, absolute cell count	10  /L	< 0.8 × LLN	> 1.5 × ULN
Hematocrit	Ratio	< 0.9 × LLN	> 1.1 × ULN
Hemoglobin	g/L	< 0.9 × LLN	> 1.1 × ULN
Platelet count	10  /L	< 0.5 × LLN	> 1.5 × ULN
Red blood cell count	10  /L	< 0.9 × LLN	> 1.1 × ULN
White blood cell count	10  /L	< 0.7 × LLN	> 1.5 × ULN
URINALYSIS			
pH	—	< 0.9 × LLN	> 1.1 × ULN
Specific gravity	—	—	> 1.1 × ULN

LLN = lower limit of normal value provided by the laboratory; SI = *Le Système International d'Unités* (International System of Units); ULN = upper limit of normal value provided by the laboratory.

### 11.3 VITAL SIGNS

Descriptive statistics for vital signs (ie, temperature, body weight, respiratory rate, supine pulse rate, supine systolic and diastolic blood pressure) and changes from baseline values at each assessment time point will be presented by study intervention group within the corresponding cohort.

Vital sign values will be considered PCS if they meet both the observed-value criteria and the change-from-baseline criteria listed in [Table 11.3–1](#). The number and percentage of participants with PCS postbaseline values will be tabulated by study intervention group within the corresponding cohort for the double-blind Intervention Period and Postintervention Period separately. The percentages will be calculated relative to the number of participants with available non-PCS baseline values and at least 1 postbaseline assessment in the specific period. The numerator will be the total number of participants with available non-PCS baseline values and at least 1 PCS postbaseline value during the specific period for the corresponding cohort. A supportive tabular display of participants with PCS postbaseline values will be provided, including the PID number, baseline and all postbaseline (including non-PCS) values.

In addition, a tabular display showing all AEs that occurred in participants who had PCS postbaseline vital sign values will be provided.

If any cohort has a similar linaclotide dose with another cohort, the above discussed vital signs summaries will also be provided combining participants from the similar dose cohorts. Summaries will also be provided for participants from all cohorts in the placebo group.

Table 11.3-1 Criteria for Potentially Clinically Significant Vital Signs

Parameter	Flag	Criteria a	
		Observed Value	Change From Baseline
Systolic Blood Pressure, mmHg - Postural Vital Signs (Supine and Standing)		Decrease in systolic blood pressure of 20 mmHg or more from supine to standing [*Change from supine SBP <= -20]	Decrease in systolic blood pressure from supine to standing at observed time point is at least 10 mmHg greater than the decrease in systolic blood pressure from supine to standing at baseline [Postbaseline change from supine SBP – baseline change from supine SBP <= -10]
Diastolic Blood Pressure, mmHg Postural Vital Signs (Supine and Standing)		Decrease in diastolic blood pressure of 10 mmHg or more from supine to standing [Change from supine DBP <= -10]	Decrease in diastolic blood pressure from supine to standing at observed time point is at least 10 mmHg greater than the decrease in diastolic blood pressure from supine to standing at baseline [Postbaseline change from supine DBP – baseline change from supine DBP <= -10]
Pulse Rate, bpm - Postural Vital Signs (Supine and Standing)		Increase in heart rate of 20 beats per minute or more from supine to standing [Change from supine pulse rate >= 20]	Increase in heart rate from supine to standing at observed time point is at least 10 beats per minute greater than the increase in heart rate from supine to standing at baseline [Postbaseline change from supine pulse rate – baseline change from supine pulse rate >= 10]
Systolic Blood Pressure, mm Hg (Supine)	High	Age 2-5 (inclusive): $\geq 125$	Increase of $\geq 20$
	Low	Age 2-5 (inclusive): $\leq 70$	Decrease of $\geq 20$
Diastolic Blood Pressure, mm Hg (Supine)	High	Age 2-5 (inclusive): $\geq 85$	Increase of $\geq 15$
	Low	Age 2-5 (inclusive): $\leq 35$	Decrease of $\geq 15$
Pulse Rate, bpm (Supine)	High	Age 2-3, boy (inclusive): $\geq 165$ Age 4-5, boy (inclusive): $\geq 133$ Age 2-3, girl (inclusive): $\geq 188$ Age 4-5, girl (inclusive): $\geq 134$	Increase of $\geq 15$
	Low	Age 2-3, boy (inclusive): $\leq 87$ Age 4-5, boy (inclusive): $\leq 63$ Age 2-3, girl (inclusive): $\leq 85$ Age 4-5, girl (inclusive): $\leq 68$	Decrease of $\geq 15$
Weight, kg	High	—	Increase of $\geq 5\%$
	Low	—	Decrease of $\geq 5\%$

a A postbaseline value is considered potentially clinically significant if it meets both the observed-value and the change-from-baseline criteria.

bpm = beats per minute; DBP = diastolic blood pressure; SBP = systolic blood pressure.

\* Change from supine value = standing value – supine value

